### Methods

#### Study population

This trial will be conducted at the pediatric outpatient clinics of Taipei Hospital, Ministry of Health and Welfare from January 1, 2021, to June 30, 2021. The inclusion criteria are children: (i) aged between 3 and 18 years; (ii) who have access to the smartphone app; (iii) with asthma treatment steps 2–4, requiring regular treatment with controller medication (for at least 6 months over the past year) according to the GINA guidelines; and (iv) who have at least two clinic or emergency department visits related to asthma in the previous year. Children who have comorbidities, or other major medical problems, and who do not have a smartphone or whose caregivers did not have a smartphone were excluded from the study.

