#### Protocol

The study enrolls 210 children to detect a 50% reduction in ACT scores, with 80% power and a 20% attrition rate. They will be randomly assigned to an intervention group and a control group. The intervention group download the asthma smartphone app, and follow up monthly via phone calls and clinic visits, while the control group receives reminder calls. At baseline, pediatric allergists examine participants using the International Study of Asthma and Allergies of Childhood (ISAAC) questionnaire. At 3 and 6 months, ACT scores, Mini Pediatric Asthma Quality of Life Questionnaire (MiniPAQLQ), Pediatric Asthma Severity Scores (PASS), Pediatric Asthma Caregiver

Quality of Life Questionnaire (PACQLQ), and peak expiratory flow (PEF) are determined by written informed consent will be obtained from the patients or their guardians. Study protocol approved by the hospital's Institutional Review Board

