### **Outcome measures**

The physician diagnoses asthma at Taipei Hospital; National Health Insurance Program retracted sociodemographic data. A retrospective chart review is used to assess the use of prescribed systemic corticosteroids (prednisolone), maintenance inhaler treatment (salmeterol/fluticasone [Seretide™, GSK Group of Companies], and anti-leukotriene treatment (montelukast). Six months before and after using the app, direct (unscheduled visits to the emergency department and hospitalization costs) and indirect costs (days off work by parents to care for their children and transportation costs) are measured, and transportation costs were estimated using a national website.

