### **Statistical analysis**

The study is used an independent t-test to compare baseline demographic data and outcome variables between intervention and control groups. The paired t-test is used to compare

intragroup scores, prescribed treatment courses, PEF changes, and medical costs 6 months before and after the intervention.

The difference-in-difference method is used to assess costs before and at 6 months between intervention and control groups. Significance is set at a two-tailed  $\alpha$  value of .05, and all analyses were conducted using SAS software version 9.1 (SAS Institute, Cary, NC, USA).

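### Name a baseline-adjusted between-arm comparison as the efficacy test for scores, PEF and treatment; the within-arm paired t-tests cannot isolate an app effect

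*SAP*

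**What the plan says.** The SAP's Protocol section randomises children to an app group or a control group that receives reminder calls. Its Statistical analysis section then sets three analyses at a two-sided .05 level:

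- Between arms: "The study is used an independent t-test to compare baseline demographic data and outcome variables between intervention and control groups". No covariate is named, and the text does not say whether follow-up values or changes are compared.
- Within each arm: a paired t-test of "intragroup scores, prescribed treatment courses, PEF changes, and medical costs 6 months before and after the intervention".
- Between arms, for costs only: "The difference-in-difference method is used to assess costs before and at 6 months between intervention and control groups".

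None of these is named as the test on which efficacy rests. Three other statements bear on the point. Entry is limited to children "who have at least two clinic or emergency department visits related to asthma in the previous year" (Study population). Costs are measured "Six months before and after using the app" (Outcome measures). The trial is dated "from January 1, 2021, to June 30, 2021" (Study population). The Protocol section lists the scores and PEF at 3 and 6 months only.

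**The concern.** There are two separate issues.

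**(a) Precision.** Under randomisation the independent t-test is valid whether it is applied to 6-month values or to changes. Adjusting for the child's own baseline is about as precise or better than either, and uses the same children. The plan uses the before value between arms for costs but not for scores, PEF or treatment courses.

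**(b) Within-arm tests.** A paired test in one arm measures every cause of change over time. Two features of this trial make change without an app effect plausible:

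- *Selection.* Children enter because they had at least two asthma visits in the past year. If app use starts at enrolment, the 6-month before window lies inside that year, so visit-driven outcomes are likely to fall afterwards through regression to the mean.
- *Season.* If the stated dates are the whole trial, 6 months of follow-up forces before windows of July to December 2020 and after windows of January to June 2021. If they are the enrolment period, each child's two consecutive half-years still cover opposite halves of a year.

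The control arm removes shared change only when the arms are compared. As written, within-arm and between-arm p values would stand side by side with no rule on which counts. A significant change in the app arm, or one in the app arm but not in the control arm, would not be evidence that the app works.

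**Working it through.** **Inputs.** From the SAP: 210 children, 80% power, 20% attrition (Protocol section); two-sided .05 (Statistical analysis). Assumed: 1:1 allocation, and the correlations, shifts, visit rates and emergency department (ED) shares shown below, since the SAP gives none.

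**1. The plan's own figure.** With no SD or baseline mean, 210 cannot be derived from the document. Working backwards, 210 × 0.8 = 168 evaluable, or 84 per arm. The detectable standardised difference is (1.960 + 0.842) × √(2/84) = 0.432 by the normal approximation. With the noncentral t it is d = 0.4348, which gives 80.0% power for an unadjusted t-test on 6-month values. That d is used in step 2.

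**2. Value of the baseline covariate.** For correlation r between baseline and 6 months, the effective standardised difference is d/√(1−r²) with baseline adjustment and d/√(2(1−r)) for a t-test on changes. The equivalent unadjusted size is 84/(1−r²); at r = 0.5, for example, 84/0.75 = 112.

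| r | t-test on values | baseline-adjusted | t-test on changes | equivalent unadjusted n per arm |
|---|---|---|---|---|
| 0.1 | 80.0% | 80.4% | 55.1% | 84.8 |
| 0.2 | 80.0% | 81.6% | 60.1% | 87.5 |
| 0.3 | 80.0% | 83.6% | 65.8% | 92.3 |
| 0.5 | 80.0% | 89.9% | 80.0% | 112.0 |
| 0.7 | 80.0% | 97.5% | 95.1% | 164.7 |

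The gain over a test of values is near nil at low correlation. The loss from testing changes is largest there, and the SAP leaves that choice open.

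**3. Paired test with no app effect: scores and PEF.** Let both arms shift by s SDs of the change. The noncentrality in one arm is s√84, and p is the resulting chance of rejection. The chance that the app arm is significant and the control arm is not is p(1−p).

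| s | one arm significant, p | app arm only, p(1−p) |
|---|---|---|
| 0.1 | 14.8% | 12.6% |
| 0.2 | 44.1% | 24.7% |
| 0.3 | 77.6% | 17.4% |

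The shift cancels between arms, so the between-arm test stays at 5%.

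**4. Regression to the mean: visits.** Visits were simulated as gamma-Poisson counts (shape 1 or 2) with no app effect. Children with at least two visits in the prior year were kept, and the last 6 months of that year were compared with the next 6 months (3,000,000 children per setting, up to 8,000 trials). The entries are the paired test's rejection rates.

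| mean visits in entry year, enrolled children | all visits | 20% are ED visits | 10% are ED visits |
|---|---|---|---|
| 2.7 | 97% | 37% | 20% |
| 3.0 | 86% | 26% | 15% |
| 3.5 | 54% | 15% | 10% |
| 4.0 | 38% | 11% | 8% |
| 4.3 | 24% | 8% | 7% |
| 5.0 | 20% | 8% | 6% |
| 6.0 | 12% | 7% | 6% |
| 7.0 | 7% | 5% | 5% |
| 8.0 | 8% | 6% | 5% |
| 10.0 | 6% | 5% | 5% |

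Across all settings run, the between-arm t-test on follow-up counts rejected in 4.4–5.5% of trials and difference-in-difference in 4.3–5.4%. Regression to the mean was not simulated for scores or PEF, nor was a cost distribution.

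**The case against.** The between-arm t-test is valid, so part (a) is about efficiency and not error. The gain is only 0.4 to 3.6 percentage points at correlations of 0.1 to 0.3. That stands, and part (a) alone would be a modest point.

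On part (b), the plan calls the paired tests intragroup, already plans randomised comparisons, and never says that the paired tests decide efficacy. Harm needs a later misreading. This is also true, but the plan has no sentence to prevent that misreading, and it gives both kinds of p value the same threshold.

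The simulated visits are a proxy. The plan pairs costs and treatment courses, not visit counts, and its direct costs are unscheduled ED visits and hospitalisation. The 97% setting also implies source children averaging about one asthma visit a year, of whom about 26% meet the entry rule. Children on regular controller treatment may attend more often, and at 7–10 visits the excess almost vanishes. The range is therefore wide and its upper end should not be read as a forecast.

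Finally, a model for each outcome does not choose a primary outcome or settle multiplicity. That is correct. A primary outcome may be named in the protocol, which was not available. The point here is which kind of comparison carries the conclusion.

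**Conclusion.** The point holds and should be fixed, with medium confidence in its size. The SAP has no baseline-adjusted between-arm test for scores, PEF or treatment courses, and it adds within-arm tests that cannot separate an app effect from shared change. The power lost depends on the correlation: negligible near 0.1, about 10 points at 0.5 and 17.5 points at 0.7, relative to a test of 6-month values back-solved to 80% power. The false-positive risk of reading a paired test as an app effect ranges from close to 5% to well above half, depending on the assumed shared shift or visit rate. The direction of the argument needs none of these assumptions; its size does. Difference-in-difference for costs is valid and is not criticised.

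**What to change.** - For each score, PEF and treatment courses, make the test of the app effect a between-arm linear model of the 6-month value on arm plus the child's own baseline (or pre-period) value, reported with its 95% CI.
- Keep difference-in-difference as the between-arm test for costs. A baseline-adjusted model may be added.
- State that conclusions rest on these between-arm estimates.
- Report within-arm changes descriptively, without p values.
- Confirm that scores and PEF are recorded before app use. The before/after tests imply it, but the SAP's Protocol section lists these measures only at 3 and 6 months; the full schedule may be in the protocol.

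The cost is SAP wording and a few lines of SAS, with no extra patients. The within-arm p values are given up. If baseline scores and PEF are not already planned, they must be added at the enrolment visit, since the model depends on them.

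### No body-size scale or covariate is set for PEF at ages 3 to 18; if raw values are used, growth alone can make the within-arm paired test significant

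*SAP*

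**What the plan says.** Four statements in the SAP bear on this.

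- **Study population:** children are eligible if "aged between 3 and 18 years".
- **Protocol:** at 3 and 6 months the questionnaire and severity scores and "peak expiratory flow (PEF) are determined". No unit, percent-predicted or personal-best scale is given, and height is not mentioned.
- **Statistical analysis, tests:** the paired t-test covers "intragroup scores, prescribed treatment courses, PEF changes, and medical costs 6 months before and after the intervention". The between-arm method is an "independent t-test to compare baseline demographic data and outcome variables between intervention and control groups". It is not said whether the between-arm test uses the 6-month level or the change from baseline.
- **Statistical analysis, difference-in-difference:** "The difference-in-difference method is used to assess costs before and at 6 months between intervention and control groups". PEF is not included.

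**The concern.** PEF rises with body size, and most children in this age range grow measurably in six months. A before-after test on raw PEF therefore has a null hypothesis of zero change that is false even if the app does nothing. Randomisation does not protect a test made inside one arm. The paired test is also the only analysis that names PEF. The SAP has a contrast that would cancel growth common to both arms, but keeps it for costs.

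A second, weaker problem concerns the between-arm test. If it compares raw 6-month levels, the spread in body size from age 3 to 18 enters the error variance and can hide a real difference.

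At stake is how a PEF result is read. A pre-post gain in the app arm could be reported as lung-function support for the self-reported scores when it reflects growth. PEF does not drive the sample size, so the trial's main comparison is not affected.

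**Working it through.** **Inputs from the SAP.** 210 children, 20% attrition, two-sided α of 0.05. Completers: 210 × 0.80 = 168, or 84 per arm. The 1:1 ratio is assumed, since none is stated. The SAP gives no PEF mean, SD, slope or growth rate, so it has no PEF figure to reproduce. The 210 is tied to ACT scores and has no bearing here.

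**Assumed PEF inputs.**
- Six-month growth gain: 4 to 6 L/min per cm × 2.5 to 3 cm = 10 to 18 L/min. A slower assumption of 10 to 30 L/min per year of age gives 5 to 15 L/min. Together: 5 to 18 L/min.
- SD of six-month change: 30 to 60 L/min.
- SD of PEF at a given body size: 40 to 60 L/min in the power calculation, 30 to 60 in the variance ratio.

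**Step 1: paired t-test within one arm, growth only, no treatment effect.** The rejection probability comes from a noncentral t with 83 degrees of freedom and noncentrality (gain / SD of change) × √84.

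| Gain (L/min) | SD of change | Noncentrality | P(significant) |
|---|---|---|---|
| 5 | 60 | 0.76 | 0.12 |
| 10 | 60 | 1.53 | 0.33 |
| 10 | 50 | 1.83 | 0.44 |
| 10 | 40 | 2.29 | 0.62 |
| 12.5 | 40 | 2.86 | 0.81 |
| 15 | 40 | 3.44 | 0.92 |
| 18 | 30 | 5.50 | >0.99 |

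Every case exceeds 0.05.

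**Step 2: one arm significant, the other not.** Growth acts in both arms, but two separate tests need not agree. With independent arms, the chance that the app arm is significant and the control arm is not is p(1 − p). At p = 0.62 this is 0.62 × 0.38 = 0.24. At p = 0.12 it is 0.12 × 0.88 = 0.11. At p = 0.92 it is 0.92 × 0.08 = 0.07. With no growth and no effect it would be 0.05 × 0.95 = 0.05.

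**Step 3: between-arm test of raw 6-month levels.** Raw SD = √[(slope × SD of age)² + residual SD²]. With ages uniform over 3 to 18, the SD of age is 15/√12 = 4.33 years. At 25 L/min per year and residual SD 50, raw SD = √(108.3² + 50²) = 119. The difference detectable with 80% power is SD × √(2/84) × (1.960 + 0.842):
- raw: 119.2 × 0.1543 × 2.802 = 51.5 L/min
- size-adjusted: 50 × 0.1543 × 2.802 = 21.6 L/min

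For an assumed true difference of 20 L/min, power is 0.19 raw and 0.74 size-adjusted. With slope 20 to 30 L/min per year, SD of age 3 to 4.33 years and residual SD 40 to 60, raw power is 0.15 to 0.44, adjusted power is 0.58 to 0.90, and body size is 50% to 91% of the raw variance.

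A height-based version agrees in direction. For heights uniform over 95 to 165 cm, the SD is 70/√12 = 20.2 cm. The ratio of raw to adjusted variance, [(slope × 20.2)² + r²]/r², runs from 2.8 (slope 4 L/min per cm, r = 60) to 17.3 (6, 30), and is 7.4 at (5, 40). Starting at 110 cm, the SD is 55/√12 = 15.9 cm and the ratio at (5, 40) falls to 4.9.

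**Step 4: between-arm test of change.** Each child's own size largely cancels. With an SD of change of 30 to 60, power for 20 L/min is 0.99 to 0.58, so most of the loss in Step 3 disappears.

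**The case against.** The strongest reply is that the SAP never says PEF is in raw L/min. It is silent on the scale, and how a lung-function measure is expressed may be set in a protocol not shown here. This stands: a reader might infer that the plan compares unscaled PEF, but the text does not say so, and the results above hold only if raw values are used. What remains is that the section assigning the tests names no scale and no covariate, so it permits raw PEF and leaves the choice open until data are seen.

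A reader might also infer that growth biases the comparison between arms. It does not. The children are randomised, so growth and body size are equal between arms in expectation, and only precision is lost. Nor can it be said that body size necessarily swamps that comparison: this applies to raw levels, not to changes, and the SAP does not say which is tested.

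A third reply is that a growth-only rise would appear in the control arm too, so nobody comparing the arms would credit it to the app. This is partly right, but Step 2 shows that separate within-arm tests can disagree by chance. It is also true that size-scaling does not make a before-after test evidence of effect, which is why the fix below does not stop at scaling.

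Finally, the magnitudes rest on assumed inputs. Mean growth of 2.5 to 3 cm in six months is high for a group that includes older adolescents; the lower end of 5 L/min allows for this.

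**Conclusion.** The point holds in conditional form. The SAP fixes a within-arm paired t-test on PEF and an unadjusted between-arm t-test for children aged 3 to 18. It sets no size-standardised scale or covariate, and it limits difference-in-difference to costs. If raw PEF is used, growth alone makes the paired test significant with probability of about 0.12 to over 0.99 instead of 0.05. A between-arm test of raw levels loses much of its power without bias; a test of changes loses far less. All PEF inputs and the 1:1 allocation are assumptions, so the direction is firm and the size is not.

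Two further inferences are not supported. One is that PEF is the only non-questionnaire measure: the SAP does not say that PASS is a questionnaire, and its Outcome measures section adds chart-reviewed medication and costs of emergency visits and hospitalisation. The other is that the youngest children cannot give a usable PEF, on which the SAP says nothing.

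This should be corrected because a better method costs little, but it does not undermine the trial.

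**What to change.** In the Statistical analysis section:

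1. Define the PEF outcome as percent predicted for height, age and sex. Name the reference equation in advance, and use height recorded at each PEF visit.
2. Base the PEF conclusion on the between-arm difference in the 6-month value, adjusted for baseline PEF on the same scale (ANCOVA).
3. State that the within-arm paired PEF tests are descriptive and are not evidence of an app effect.

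The cost is a height measurement at visits already planned and a change of analysis variable. The ANCOVA needs a baseline PEF. The before-after paired test already presupposes one, although the Protocol section lists PEF only at 3 and 6 months, so the baseline measurement should be stated. No change in sample size or eligibility is needed.

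### The paired t-tests of treatment courses and costs start from a before-window that entry partly selects to be high, so a within-arm fall can reach significance with no app effect; the between-arm comparison is sound but is not tied to the before-value for courses.

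*SAP*

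**What the plan says.** **Entry.** Under Study population, the SAP admits children at treatment steps 2 to 4 "requiring regular treatment with controller medication (for at least 6 months over the past year") and "who have at least two clinic or emergency department visits related to asthma in the previous year". The trial runs "from January 1, 2021, to June 30, 2021"; the text does not say whether that is the recruitment period or the whole conduct.

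**Windows.** Under Outcome measures, costs are measured as follows: "Six months before and after using the app, direct (unscheduled visits to the emergency department and hospitalization costs) and indirect costs". Prescribed courses of systemic steroid, combination inhaler and montelukast come from chart review.

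**Tests.** Under Statistical analysis there are three, all at a two-sided .05, with no ranking and none labelled descriptive:
- a paired t-test within each group of "intragroup scores, prescribed treatment courses, PEF changes, and medical costs 6 months before and after the intervention";
- an "independent t-test to compare baseline demographic data and outcome variables between intervention and control groups";
- for costs only: "The difference-in-difference method is used to assess costs before and at 6 months between intervention and control groups".

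**The concern.** The six months before the app are the later half of the year on which entry is decided. A child who happened to need more care in that year is more likely to enter; nothing selects on the six months afterwards. The paired test takes no change as its null, but selection alone makes some fall likely. What is tested also lies close to what is selected. Emergency visits count both towards entry and towards cost, and the maintenance drugs among the courses are the kind of treatment that the controller criterion requires.

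Season is a second, separate source of shift. For any one child the two windows are consecutive half-years and so cover different calendar months, and no seasonal adjustment is planned.

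At stake is how the within-arm p-values are read. A significant fall in the app arm, or a fall that is significant there and not in the control arm, could be taken as an effect of the app when it reflects who was admitted.

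**Working it through.** **The plan's own figure.** The SAP states: "The study enrolls 210 children to detect a 50% reduction in ACT scores, with 80% power and a 20% attrition rate". It gives no SD, baseline mean or baseline rate, so 210 can be neither reproduced nor refuted. It is used here only for the arm size: 210 × 0.8 = 168, and 168 / 2 = 84 per arm, assuming 1:1 allocation.

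**Inputs.** From the SAP: entry at 2 or more visits in 12 months, before-window the last 6 of those months, after-window the next 6, two-sided α .05 (so 2.5% for a fall). Assumed: the mean yearly visit count *m* before selection; gamma variation between children with shape *k*; Poisson counts given the child's rate; and the share of visits that generate a course or cost. The app has no effect. Only the visit criterion is modelled; selection on controller treatment is not.

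**Size of the spurious fall, worked for *m* = 3, *k* = 2.** Let T be the count in the year before entry.
- P(T=0) = (k/(k+m))^k = (2/5)² = 0.160
- P(T=1) = k × m/(k+m) × P(T=0) = 2 × 0.6 × 0.160 = 0.192
- Share eligible = 1 − 0.160 − 0.192 = 0.648
- E[T | T≥2] = (3 − 0.192)/0.648 = 4.333, so the before-window mean is 4.333/2 = 2.167
- E[rate | T] = (k+T) × m/(k+m), so the mean rate given T≥2 is 0.6 × (2 + 4.333) = 3.80, and the after-window mean is 3.80/2 = 1.90
- Fall = 1 − 1.90/2.167 = 12.3%

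Simulation of the same setting gives 2.165, 1.901 and 12.2%. If only a share of visits generates the outcome, the percentage fall is unchanged, but there are fewer events, so the paired test detects it less often.

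**How often the paired test shows a false significant fall in one arm** (simulated, *k* = 2, 84 per arm):

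| Visits per year before selection | Fall in mean | 40% of visits generate the outcome | 15% do |
|---|---|---|---|
| 1.5 | 29% | about 38% | about 17% |
| 2 | 21% | 23% | about 13% |
| 3 | 12% | 13% | about 7% |
| 4 | 8% | 7.5% | about 6% |
| 6 | 4% | 4% | about 4% |

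Over shapes 1 and 2 and means 1.5 to 4, the range is 6% to 38% at a 40% share and 5% to 17% at a 15% share. With skewed (lognormal) costs at a 15% share, means 2, 3 and 4 give about 7%, 4% and 3%, with simulation error of about 1 point. With neither selection nor season (mean 3, all visits counted), the test returns 2.3%, so the excess comes from the entry rule.

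**App arm significant, control arm not.** With independent arms and no effect this has probability p(1−p). At a 40% share and means 2, 3 and 4: 0.234 × 0.766 = 18%, 0.126 × 0.874 = 11%, 0.075 × 0.925 = 7%. Nominally: 0.025 × 0.975 = 2.4%.

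**Season alone** (no selection, mean 3, all visits counted): an assumed after/before rate ratio of 0.8 gives a significant fall in 40% of arms; a ratio of 1.25 gives a significant rise in 41%.

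**Between-arm test of change.** Type I error stays at 4.2% to 5.5% in all settings, with selection, season or both.

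**The case against.** Much of the case on the other side stands.

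- *The tested outcomes are not visit counts.* The paired sentence does not list visits. Direct costs cover unscheduled emergency visits and hospitalisation, whereas routine clinic visits can satisfy entry. Simulating all visits gives a false fall in 12% to 77% of arms over means 1.5 to 4. A reader might carry that figure over, but it does not describe courses or costs.
- *The threshold may hardly bind.* Children on controllers for at least half the year may attend often. At 6 visits per year the excess nearly disappears. The SAP does not give the rate, so neither a large nor a negligible size can be excluded.
- *Season has no known direction.* One might infer that season makes a false fall nearly certain. That needs an assumed seasonal ratio, a busier before-window and all children starting together, none of which the SAP states. If entry is staggered over January to June, the pooled windows overlap in calendar time and the contrast softens.
- *The right analysis for costs is already there.* Difference-in-difference is planned for costs and an independent t-test for outcome variables. Nothing in the SAP makes the paired tests the basis for a claim of benefit or saving.

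The objection does not rescue the paired test itself, whose null need not hold when the app does nothing. Nor does it close the gap for courses, where the paired test is the only stated analysis that uses the before-value.

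**Conclusion.** The point holds, confined to the within-arm paired tests of treatment courses and medical costs. The mechanism follows from the SAP's own entry criteria and windows; the size does not. It rests on assumed visit rates, between-child variation, event shares and 1:1 allocation: about 5% to 38% false significant falls per arm at 1.5 to 4 visits per year, about 3% to 5% at 6, and less for skewed costs. Rarer visits would make it worse: at 1 visit per year and a 40% share, shapes 1 to 5 give 48% to 80%. The unmodelled controller criterion could add to the selection on maintenance courses.

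A reader might infer that the trial's estimate of cost saving is biased. The documents do not support that: both arms are selected by the same rule and, through randomisation, share the calendar, so the between-arm comparison is valid.

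**What to change.** 1. Remove prescribed treatment courses and medical costs from the paired t-test sentence.
2. Base inference for both on the between-arm comparison using the before-window value: keep difference-in-difference for costs and extend it to courses, or use a between-arm model adjusted for the before-value.
3. If before/after figures are shown, give both arms side by side without p-values.

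Comparing with the same six calendar months of the previous year is not a remedy. It would remove season, but that half-year belongs to the same selected year. Entry depends on the sum of the two halves, so the spurious fall is the same for either (29%, 21% and 12% at means 1.5, 2 and 3). Its costs also lie outside the planned measurement window.

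The change is to SAP wording only and needs no new data. The sponsor gives up within-arm p-values for courses and costs.

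### The difference-in-difference cost comparison is valid but less precise than adjusting for the pre-period cost the trial already collects

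*SAP*

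**What the plan says.** On design, the SAP (Protocol) states: "They will be randomly assigned to an intervention group and a control group". The allocation ratio is not given.

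On what is measured, the SAP (Outcome measures) sets equal windows: "Six months before and after using the app, direct (unscheduled visits to the emergency department and hospitalization costs". It adds that "indirect costs (days off work by parents to care for their children and transportation costs) are measured". A pre-period cost is therefore collected.

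On analysis, the SAP (Statistical analysis) states: "The difference-in-difference method is used to assess costs before and at 6 months between intervention and control groups". The test is two-sided at .05. The same section uses a paired t-test for within-group changes in medical costs and an independent t-test for baseline data and outcome variables. It does not say whether costs are among those outcome variables. No cost model with pre-period cost as a covariate is named.

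On size, the SAP (Protocol) states: "The study enrolls 210 children to detect a 50% reduction in ACT scores, with 80% power and a 20% attrition rate". That calculation concerns ACT, and none is given for costs.

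**The concern.** Difference-in-difference is built for groups that may differ systematically at the start. Randomisation gives pre-period cost the same expectation in both arms, so only chance imbalance remains. Subtracting the whole pre-period cost over-corrects for that imbalance unless the regression of post on pre has a slope of 1. The excess correction adds variance to the estimate.

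A weak relation between the two periods is plausible here. The listed direct costs are emergency visits and hospital stays, which are episodic. Entry asks for children "who have at least two clinic or emergency department visits related to asthma in the previous year", so a child can qualify on clinic visits alone and have no emergency or hospital cost in the six months before. At stake is a wider interval than the data allow, and a real saving that may be reported as not significant.

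**Working it through.** **Plan's own figure.** 210 × (1 − 0.20) = 168, or 84 per arm at 1:1. The standardised difference detectable with 80% power is (1.960 + 0.842) × √(2/84) = 0.43. The SAP gives no ACT mean or SD, so 210 can only be back-solved, not reproduced, and it says nothing about costs. I use 84 per arm below.

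**Inputs from the SAP.** Randomised two-arm design, six-month pre and post windows, two-sided .05.

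**Assumed.** 1:1 allocation; pre-period cost measured over comparable pre-randomisation months in both arms; rho from 0 to 0.7; ratio k of pre-period to post-period SD of 1, 1.5 or 2.

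**Variances.** Let s be the post-period SD and ks the pre-period SD. Per child:
- Difference-in-difference: s²(1 + k² − 2·rho·k)
- Covariate adjustment: s²(1 − rho²)
- Gap: s²(k − rho)², which is never negative and is zero only when k = rho, that is, when the slope of post on pre is 1.

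With k = 1 the ratio is 2(1 − rho)/(1 − rho²) = 2/(1 + rho).

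**Power where adjustment has 80%.** Power = Φ(2.802/√ratio − 1.960). For rho 0.2: 2.802/√1.667 − 1.960 = 0.210, and Φ(0.210) = 58%.

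| rho | variance ratio (k = 1) | difference-in-difference power |
|---|---|---|
| 0 | 2.00 | 51% |
| 0.2 | 1.67 | 58% |
| 0.4 | 1.43 | 65% |
| 0.5 | 1.33 | 68% |
| 0.7 | 1.18 | 73% |

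With k = 1, difference-in-difference retains at least 56% of the adjusted power, whatever the adjusted power between 10% and 90%. With k = 1.5 the 80% becomes 34% at rho 0 and 39% at rho 0.2. With k = 2 it becomes 24% to 29% over rho 0 to 0.7.

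Against ignoring the pre-period altogether, the ratio is 2(1 − rho) at k = 1. Difference-in-difference is therefore worse than a post-only comparison below rho 0.5 and better above it.

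**Simulation with skewed costs.** All distributional inputs are assumed: 84 per arm, 30% of children with any cost falling to 15% under the app, lognormal amounts with log-SD 1, HC3 errors for the adjusted model.

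| rho | adjusted | difference-in-difference | ratio of powers |
|---|---|---|---|
| 0 | 31% | 15% | 0.48 |
| 0.19 | 31% | 17% | 0.55 |
| 0.42 | 35% | 22% | 0.63 |
| 0.68 | 47% | 36% | 0.77 |

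Null rejection was about 4–6% for both. The loss at rho 0 exceeds the equal-SD result at 30% adjusted power (17%, ratio 0.57) because the simulated effect also shrinks post-period spread in the app arm. In a further run with 50% of children having pre-period cost, adjusted power was 31–33% and difference-in-difference 13–16% at the low correlations tried.

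**The case against.** The strongest reply is that nothing is wrong here: difference-in-difference is unbiased under randomisation, its false-positive rate is near nominal, and the trial is sized on ACT. That stands, and it limits the point to efficiency. A reader might infer that the cost result would be biased or invalid; the SAP does not support that.

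Second, the size is not documented. A reader might infer that costs are zero-heavy and weakly correlated, and hence that the method halves power. The SAP gives no SD, zero share or correlation. Indirect costs may behave differently from emergency and hospital costs, and persistent severity among children needing regular controller treatment could raise the correlation. At moderate rho the loss is real but well short of half.

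Third, it is tempting to say that adjustment is never less precise. Without an arm-by-baseline interaction, that asymptotic result needs equal allocation or equal slopes in the two arms, and the SAP states no ratio. The caveat stands and is met in the fix.

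Fourth, the independent t-test on outcome variables might already supply a post-period cost comparison, which at low rho would perform about as well as adjustment. The text does not assign costs to that test and names difference-in-difference for them, so this cannot be relied on.

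**Conclusion.** The point holds as an efficiency improvement. In this randomised trial the planned cost comparison is less precise than adjustment for a covariate already in hand, except in the special case where the post-on-pre slope is 1. The direction needs no assumption about the shape of the cost distribution, given 1:1 allocation or equal slopes.

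The size does need assumptions. With equal SDs, 80% power under adjustment corresponds to about 51–65% under difference-in-difference for rho 0 to 0.4, and 68% at rho 0.5. About half or less arises only with low correlation or with pre-period costs more variable than post-period costs. Either is possible here, but neither is shown by the SAP. In the skewed scenarios simulated, cost power was modest under both methods.

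**What to change.** Replace the difference-in-difference sentence in the SAP (Statistical analysis) with text along these lines: *The between-group cost difference will be estimated by linear regression of six-month post-period cost on arm and pre-period cost, with HC3 standard errors, and reported as the adjusted arithmetic mean difference with its 95% confidence interval. If allocation is not 1:1, pre-period cost will be centred and an arm-by-pre-period-cost interaction included. Difference-in-difference will be reported as a sensitivity analysis.* State the allocation ratio in the same revision.

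The cost is a few sentences of text and a few lines of code, with no new data and the same mean difference as target. The small downside is that intervals from the adjusted model can under-cover slightly when costs are extremely skewed: coverage was 90–93% in the harshest simulated cases with an uncorrected sandwich error. That is the reason for HC3 and for keeping the sensitivity analysis.
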